### 12.5 MULTI-CENTER ADJUSTMENT

Multiple centers/sites will contribute data to this study. Given the variance in standard of care between sites, the primary analysis will be adjusted for site variability. This will be done by including a categorical site covariate in the primary analysis model. The secondary [REDACTED] objectives will not be adjusted for site.

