## 2.0 ABBREVIATIONS AND TERMS

- AE – Adverse Event
- CRO – Contract Research Organization
- CTF – Cut-to-fit; a barrier hole opening that is cut to size.
- DET score; Validated Ostomy Skin Tool [1]. The DET score assesses Discoloration, Erosion, and Tissue Overgrowth of the peristomal skin.
- eCRF – Electronic Case Report Form
- EDC – Electronic Data Capture; a method used for electronic documentation of study procedures and data.
- EC – Ethics Committee
- HIPAA – Health Insurance Portability and Accountability Act; a US law designed to provide privacy standards to protect patients' medical records and other health information provided to health plans, doctors, hospitals and other health care providers.
- IRB – Institutional Review Board
- MEDDEV – Medical Device Directives (guidance documents) provided by the European Commission
- Peristomal Skin; the skin covered by the adhesive portion of the pouching system (barrier and tape).
- PSC – Peristomal Skin Complication; For the purposes of this study, a peristomal skin complication, is defined as a DET score of greater than 0 due to anything other than normal post-operative healing and/or scar tissue, or an increase in the subject's DET score as compared to the DET score at the prior visit as determined by a study investigator.
- PHI – Protected Health Information; any information about health status, provision of health care, or payment for health care that can be linked to a specific individual.

- **Stoma-related cost;** costs assigned to utilization data accrued through the duration of the study period (including both [REDACTED] and [REDACTED]). This includes treatments related to stoma and/or PSCs (topical medications, clinic visits, accessory use, etc.), social impact of stoma and/or PSCs (e.g. missed work/appointments), hospitalizations, ER visits, physician/clinic visits, ostomy-related medication use and therapies, and barrier utilization.

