## 7.0 STUDY DESIGN

The study is multi-center, randomized, controlled, double-blinded, and utilizes an adaptive design.

Subjects who meet the Eligibility Criteria (listed in Sections 8.1 and 8.2) are enrolled and randomized to Arm 1 or Arm 2 during the Initial [REDACTED] Visit. The assigned Arm and the study barrier are double blinded. All subjects receive standard clinical management of stoma needs as per the Investigator's usual practices. Subjects are initially enrolled into the [REDACTED] which consists of two study visits after enrollment [REDACTED]. If the subject develops a PSC, as defined as a DET score greater than 0 due to anything other than normal post-operative healing and/or scar tissue, or an increase in the subject's DET score as compared to the DET score at the previous visit, prior to the end of the [REDACTED], the subject will be immediately moved to the four (4) week [REDACTED].

which consists of two study visits [REDACTED]. Thus, the total possible time of participation in the study is up to 12 weeks and up to 5 scheduled study visits.

Subjects in Arm 1 are assigned to the [REDACTED] barrier (Test) and subjects in Arm 2 are assigned to either the [REDACTED] barrier (Control).

Study visits consist of a physical evaluation and photography of the stoma area with the pouching system removed [REDACTED], a structured interview by the investigator or designee [REDACTED], and subject completion of a paper or online Quality of Life questionnaire [REDACTED] provided in the subject's local language. The duration of each study visit is approximately 30 minutes.

In support of the primary objective, the following utilization information is collected to support cost of care calculations: utilization of treatments related to stoma and/or PSCs (topical medications, clinic visits and accessory use), social impact of stoma and/or PSCs (missed work/appointments), stoma and/or PSC related hospitalizations, ER visits, physician/clinic visits, medication use and therapies, and barrier utilization (not including pouch utilization). This data is collected at each study visit through the use of [REDACTED] and may include documentation on [REDACTED].

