#### 9.5 METHOD OF ASSIGNING PATIENTS TO STUDY ARMS

Subjects are randomized to Arm 1 (test barrier) or Arm 2 (control barrier) and assigned either study barriers [REDACTED] via a randomized block design stratified by study site and arm. The control barrier material is [REDACTED], depending on the Investigator's standard of care and the subject's needs, and the test barrier material is [REDACTED].

Central randomization is performed within the EDC system [REDACTED]

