### 12.4 COVARIATE ADJUSTMENT

The primary statistical analysis of total cost of care will be adjusted for, obesity (defined via BMI), ostomy type, stomal age (defined as weeks after surgery), and presence of a hernia. This is to account for the potential variability in the data induced by these covariates. All other analyses will be unadjusted.

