## 13.0 STATISTICAL ANALYSIS

### 13.1 ANALYSIS OF PRIMARY OBJECTIVE

Total cost of care is defined as all stoma related costs accrued through the duration of the study period. Health care resource utilization data collected to support this objective includes treatments related to stoma and/or PSCs (topical medications, clinic visits, accessory use, etc.), social impact of stoma and/or PSCs (e.g. missed work/appointments), hospitalizations, ER visits, physician/clinic visits, ostomy-related medication use and therapies, and barrier utilization (not including pouch utilization). [REDACTED]

[REDACTED] A corresponding country specific unit cost or reasonable estimate (when data is not available) will be assigned to each of the health care resource units listed above. Total cost of care will be calculated by multiplying the units of health care resources by the corresponding country specific resource unit cost and then summing costs across the study period.

The primary objective will be analyzed via an analysis of covariance (ANCOVA) model comparing the mean daily total cost of care between the treatment ([REDACTED]) and control ([REDACTED]) arms. The model will be adjusted for the covariates listed in Section 12.4, site location, and relevant demographic variables. Formally, the null and alternative hypotheses being evaluated are:

- a) Null: No difference in the mean total cost of care for 12 weeks between [REDACTED] and control i.e.  $H_0: \mu_{Test} = \mu_{Control}$  vs.
- b) Alternative: The mean total cost of care for 12 weeks for [REDACTED] is not equal to that of the control i.e.  $H_A: \mu_{Test} \neq \mu_{Control}$ .

[REDACTED]

[REDACTED]

3. Given assumptions 1 and 2, this results in a difference in mean total cost of care for the [REDACTED] and control arms of [REDACTED].
4. Using Meisner's costs of PSC according to level of severity [REDACTED] for 50% of the population, the estimate of the standard deviation for total cost of care is [REDACTED]

Using the estimates above the sample size required for to achieve 80% power with a 2.5% type 1 ( $\alpha$ ) error would be 72 per arm completed for the primary endpoint and 93 completed per arm for the secondary endpoint. In order to cover both primary and secondary endpoints, an initial sample size of 93 completed per arm was chosen. Based on the findings of the first interim analysis with 92 subjects [REDACTED] the sample size has been increased to 105 subjects per arm.

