### 13.5 INTERIM ANALYSIS

Given the uncertainty in the effect size estimates used to create the initial sample size requirement, this study employs an adaptive design. While the initial sample size was estimated based on available published data, the impact [REDACTED] will have in this population is not well known. Due to this limited knowledge, the data was analyzed once 92 subjects [REDACTED] were completed in each arm. Based on the interim findings it was determined that [REDACTED] and the sample size requires an increase to 105 subjects per arm to maintain 80% conditional power. [REDACTED]

[REDACTED] To allow for early stopping and a re-evaluation of sample size an additional interim analysis will be performed once 76( $\pm$ 5) subjects per arm have completed. The general approach of the adaptive design has been derived from Mehta and Pocock [6]. [REDACTED]

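### Randomisation is blocked within site but PSC incidence is analysed without site: the test stays valid, but it is conservative and gives up some power if sites differ in PSC risk

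*Combined protocol and SAP*

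**What the plan says.** Section 9.5 assigns subjects to the two arms "via a randomized block design stratified by study site and arm". Arm is what is being assigned and cannot itself be a stratum, so I read this as blocks within site.

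Section 12.5 gives a reason for using site in the primary analysis: "Given the variance in standard of care between sites, the primary analysis will be adjusted for site variability". The same section then says "The secondary [REDACTED] objectives will not be adjusted for site". Section 12.4, after listing the covariates for the cost model, ends with "All other analyses will be unadjusted". PSC incidence is the secondary objective (section 5.2), so its comparison contains neither site nor any covariate.

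Three places bear on whether PSC risk could vary by site:

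- Section 2.0: an increase in DET score counts as a PSC "as determined by a study investigator".
- Section 7.0: "All subjects receive standard clinical management of stoma needs as per the Investigator's usual practices".
- Section 9.5: the control barrier material depends on the investigator's standard of care.

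On sample size, section 13.1 gives 72 completed per arm for cost and "93 completed per arm for the secondary endpoint", at 80% power and 2.5% alpha. The number was later raised to 105 per arm. Sections 13.2 to 13.4 are not visible in the public text, so the exact secondary test cannot be read. Nothing that is visible puts site back into it.

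**The concern.** Blocking within site makes the arms nearly equal in size at every site, so differences between sites largely cancel from the treatment contrast. A test that ignores site still counts those differences as noise. If PSC risk varies by site, the estimated standard error exceeds the true one, and the test rejects less often than its nominal level under the null and less often than it could under the alternative.

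The protocol accepts this reasoning for cost and gives no visible reason for not applying it to PSC incidence. PSC incidence set the initial sample size (93 against 72 per arm) and carries a Bonferroni correction (section 12.6), so alpha left unused there is a real loss.

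The point concerns site only. Obesity, ostomy type, stomal age and hernia are not listed as stratification factors, and leaving them out does not make the test conservative.

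**Working it through.** **Inputs from the protocol.** Blocks within site (9.5); no site term for the secondary (12.4, 12.5); 80% power, alpha 2.5% and 93 per arm, later 105 (13.1).

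**Inputs assumed.** The public text does not show PSC rates, number of sites, block size, between-site spread or the secondary test. I took a two-sided Pearson (pooled two-proportion) test, 1:1 allocation, blocks of 4, and 12 or 20 sites of equal or unequal size.

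**Step 1: rates that fit the stated 93 per arm.**

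n = [z(α/2)·√(2p̄q̄) + z(β)·√(p₁q₁ + p₂q₂)]² / (p₁ − p₂)²

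For 50% vs 28%, p̄ = 0.39:

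- √(2 × 0.39 × 0.61) = 0.690
- √(0.25 + 0.2016) = 0.672
- n = (2.241 × 0.690 + 0.842 × 0.672)² / 0.22² = 92.1, so 93 per arm

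Power is Φ[(0.22√n − 2.241 × 0.690)/0.672]. That is Φ(0.856) = 80.4% at 93 per arm and Φ(1.054) = 85.4% at 105. Other pairs also give 93, for example 40% vs 19.4%, or 50% vs 30% at one-sided 0.025. The stated figure is plausible but cannot be verified.

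**Step 2: direction and rough size by formula.** Let f be the share of the outcome variance p(1 − p) that lies between sites. With perfect balance within site, the true variance of the contrast is about (1 − f) times what the unadjusted test uses. Its actual two-sided level is then about 2[1 − Φ(2.241/√(1 − f))]. For a 50% rate:

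| Site SD (logit) | f | Formula level | Simulated, unadjusted (10 or 20 sites, 93 per arm) |
|---|---|---|---|
| 0.5 | 0.056 | 2.1% | 2.1–2.2% |
| 1.0 | 0.174 | 1.4% | 1.5% |
| 1.5 | 0.293 | 0.8% | 0.9–1.0% |

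The simulated levels lie at or slightly above the formula, as expected when incomplete blocks leave the balance imperfect. None exceeds 2.5%.

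**Step 3: simulation at 105 per arm.** There were 20,000 trials per cell, with normal site intercepts on the logit scale and marginal rates held at 39/39 (null) and 50/28 (alternative). The unadjusted Pearson test and the site-stratified Cochran-Mantel-Haenszel (CMH) test, without pooling or continuity correction, were run on the same simulated trials at two-sided 0.025. The site range is one SD either side of 39% on the logit scale; for SD 1.0, logit(0.39) = −0.447, and −1.447 and 0.553 convert back to 19% and 63%.

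| Site SD | Site range | Type I, unadjusted | Type I, CMH | Power, unadjusted | Power, CMH | Change in power (points) |
|---|---|---|---|---|---|---|
| 0 | none | – | – | 85.2–85.6% | 84.4–85.2% | −0.8 to −0.3 |
| 0.25 | 33–45% | – | – | – | – | −0.5 to +0.1 |
| 0.5 | 28–51% | 2.0–2.3% | 2.3–2.7% | 85.8–86.3% | 86.7–87.3% | +0.6 to +1.0 |
| 1.0 | 19–63% | 1.5–1.6% | 2.5–2.6% | 87.2–87.4% | 90.6–91.3% | +3.4 to +3.9 |

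A dash marks a figure not reported here. Monte Carlo standard error is about 0.1 point for type I error and 0.25 point for power. Break-even lies between SD 0.25 and 0.5.

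**Step 4: other settings.** Separate runs gave the same pattern. With 26 uneven sites, the most that the single-letter site codes in section 9.2 suggest, the change was −1.1, +0.3 and +3.0 points at SD 0, 0.5 and 1.0. With 40% vs 19.4% and SD 1.0, power was 87% unadjusted against 90% stratified. Interim looks and dropout were not modelled.

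**The case against.** The strongest reply is that this is a preference about efficiency. Sections 12.4 and 12.5 state the unadjusted choice openly and agree with each other, the test is valid, and in every scenario above it has at least 85% power at 105 per arm. The gain of more than 3 points needs site PSC rates spread over roughly 19% to 63%, and no visible text supports a spread that wide. Cost should vary by site more than PSC does, because it is built from local resource use and country-specific unit costs, whereas PSC is scored on a validated tool in subjects who enter with normal peristomal skin. The secondary test is not visible, so a prescribed CMH test might clash with unseen text. An interim analysis has already led to a larger sample, so changing the test now invites questions. Finally, the simulated CMH test did not pool small sites, as the proposed one would.

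Much of this stands. The gain is conditional and its size is unknown; at modest site differences it is nil or about a point. That limits the weight of the point but leaves its direction intact, and the investigator's judgement in calling a PSC still leaves room for site differences.

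The pooling objection has a small effect. With sites under 10 subjects pooled, the gain at SD 1.0 was about 2.8 points with 20 sites (type I error about 2.2%) and about 3.8 with 12 uneven sites. With sites under 8 pooled, the loss at SD 0 was 0.2 to 0.4 points.

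The timing objection is met only if those who decide are documented as blinded. One gap remains: if the control material changes the treatment effect by site, a common risk difference averages over that, and the simulation varied site intercepts only.

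**Conclusion.** The concern holds as an efficiency point. The design balances on site, the protocol expects sites to differ in care, and the PSC comparison omits site. If sites differ in PSC risk, the planned test is conservative: at a nominal 2.5% it runs at about 2.0–2.3% for a site SD of 0.5 and 1.5–1.6% for an SD of 1.0. Stratifying costs up to about 1 point of power if sites do not differ, and returns 3 to 4 points if they differ widely.

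These sizes rest on the assumed rates, site numbers, block size and Pearson test. Type I error is not inflated and no shortfall from 80% power is shown. The change is worth making, with medium confidence in its size.

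**What to change.** In section 12.5, replace the sentence for PSC incidence with wording such as:

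> PSC incidence will be compared with a Cochran-Mantel-Haenszel test stratified by site, with the Mantel-Haenszel common risk difference as the estimate. Very small sites are pooled by a rule fixed in advance. The unadjusted comparison is a sensitivity analysis.

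In section 12.4, end with:

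> All other analyses will be unadjusted, except that PSC incidence is stratified by site (section 12.5).

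The sponsor should check both against sections 13.2 to 13.4. Section 13.5 plans a further look ("To allow for early stopping and a re-evaluation of sample size an additional interim analysis will be performed once" 76 ± 5 per arm have completed). Staff without access to unblinded results should fix the change and the pooling rule before that look, and the amendment should say so. If that blinding cannot be documented, keep the planned test and add the site-stratified one as a pre-specified sensitivity analysis.

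The cost is one sentence in each of two sections and a pooling rule. No new data are needed, since the subject identifier already carries the site (section 9.2). Adjustment for the section 12.4 covariates is optional and separate.

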## 12.6 MULTIPLE COMPARISONS AND MULTIPLICITY

[REDACTED]),  
Dunnnett's test, [REDACTED] will be used to assess whether there is any significant difference between [REDACTED] as they relate to the primary objective. A Bonferroni correction will be used to adjust the secondary endpoint. All other analytical results, unless explicitly stated, will be assessed against an unadjusted alpha of 0.05.

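### Do the 2.5% in the sample size and the Bonferroni rule in Section 12.6 force either an inflated familywise error or an underpowered secondary endpoint?

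*Combined protocol and SAP*

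**What the plan says.** Section 12.6 makes three statements. The first, largely blacked out, assigns Dunnett's test to comparisons under the primary objective. The second is "A Bonferroni correction will be used to adjust the secondary endpoint", with no divisor or resulting level visible. The third says that remaining results, where nothing else is specified, "will be assessed against an unadjusted alpha of 0.05".

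The sample-size paragraph printed under Section 13.1 aims to "achieve 80% power with a 2.5% type 1" error and arrives at "72 per arm completed for the primary endpoint and 93 completed per arm for the secondary endpoint". To cover both endpoints, "an initial sample size of 93 completed per arm was chosen". Sections 13.1 and 13.5 then report an increase to 105 per arm after the first interim analysis. The primary alternative is two-sided: mean cost on the test barrier "is not equal to that of the control".

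The mean difference, the standard deviation and the complication rates behind 72 and 93 are not visible. The visible section numbers jump from 13.1 to 13.5, so no section on the secondary analysis can be read.

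**The concern.** A Bonferroni split over two endpoints protects the familywise error only if both are tested at the reduced level. Section 12.6 names only the secondary endpoint, and its one visible number is 0.05. A reader who takes Dunnett's test to concern only multi-group comparisons may conclude that the two-arm primary ANCOVA falls under that 0.05. The 2.5% in the sample size then looks out of place.

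- If 2.5% is two-sided, the primary seems to be sized at 2.5% but tested at 5%, so the two levels add to 7.5%.
- If 2.5% is one-sided, that is two-sided 5%, the 93 per arm seems to leave out the correction that Section 12.6 imposes, and the secondary is underpowered.

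The stakes would be real. The secondary endpoint fixed the initial size of the trial, and a p-value between 0.025 and 0.05 would count as success or failure depending on the reading.

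**Working it through.** **Inputs.** From Section 13.1: type I error 2.5%, power 80%, 72 and 93 completed per arm, later 105. From Section 12.6: Bonferroni for the secondary endpoint, 0.05 for residual analyses. Equal allocation is inferred from the equal numbers per arm. Normal quantiles: z(0.975) = 1.9600, z(0.9875) = 2.2414, z(0.80) = 0.8416.

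**Can 72 and 93 be reproduced?** Not independently, because the effect sizes are redacted. Back-calculation with d = (z_α + z_0.80)·√(2/n) gives:

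- 2.5% two-sided: z sum 2.2414 + 0.8416 = 3.0830, so d = 0.514 for n = 72 and 0.452 for n = 93.
- 2.5% one-sided: z sum 1.9600 + 0.8416 = 2.8016, so d = 0.467 for n = 72 and 0.411 for n = 93.

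With assumed complication rates, 50% versus 30% gives 93 per arm at one-sided 2.5%, and 50% versus 28% gives 93 at two-sided 2.5%. The figure of 93 therefore does not reveal the sidedness.

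**Power of the secondary endpoint.** If 93 per arm gives 80% at the sizing level, power at n per arm and testing quantile z_t is Φ(z sum · √(n/93) − z_t), with √(105/93) = 1.0626.

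- Sized and tested at two-sided 2.5%: Φ(3.0830 − 2.2414) = 80.0% at 93; Φ(3.2759 − 2.2414) = 85.0% at 105.
- Sized at one-sided 2.5%, tested at two-sided 2.5%: Φ(2.8016 − 2.2414) = 71.2% at 93; Φ(2.9769 − 2.2414) = 76.9% at 105. Restoring 80% would take 93·(3.0830/2.8016)² = 112.6, or 113 per arm.
- Sized at two-sided 2.5%, then halved again to two-sided 1.25%: 72.1% at 93 and 78.2% at 105.

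**Familywise error over the two endpoints.** The upper bound is the sum of the levels; under independence it is 1 − (1 − α₁)(1 − α₂).

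| Primary tested at | Secondary tested at | Upper bound | If independent |
|---|---|---|---|
| 2.5% | 2.5% | 5.0% | 4.94% |
| 5% | 2.5% | 7.5% | 7.38% |
| 2.5% | 1.25% | 3.75% | 3.72% |

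**Which reading does the text support?**

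1. Section 13.1 applies one level, 2.5%, to both endpoints, and 5%/2 = 2.5%. With one primary and one secondary endpoint, that is the Bonferroni share. The first row of the table and the first power line follow: at most 5.0% error, 80% power.
2. The 7.5% needs the primary to be tested at 5%. The 0.05 sentence covers what is left after separate sentences on the primary objective and the secondary endpoint, so on its ordinary meaning it covers neither. The only level visible for the primary is 2.5%. A two-sided alternative is fully compatible with a two-sided 2.5% test.
3. The 71% needs three conditions together: a one-sided 2.5%, a correction not yet included in it, and 93 per arm. The first two are not stated, and the third has been superseded.

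The powers at 105 are fixed-design figures that ignore the interim analyses.

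**The case for a change.** The strongest case for the concern is that the two sections are never tied together in the visible text. Section 12.6 limits the correction to the secondary endpoint, no sentence gives the level of the primary ANCOVA, and the 2.5% carries no sidedness. Dunnett's test compares several groups with one reference and does not by itself share alpha between a cost endpoint and a skin endpoint. One-sided 2.5% is also a common shorthand for two-sided 5%. An analyst with only these words could test the primary at 5%. The arithmetic behind 7.5%, 71.2%, 76.9% and 113 is correct on its own premises.

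The missing details do stand as missing from what can be read. They do not show an error. The opening of Section 12.6 is blacked out around Dunnett's test, which is where the primary's testing level would be expected. Section 7.0 describes the control arm in words that suggest more than one control material, so Dunnett's test may well belong to the primary comparison. The secondary endpoint's level and family size may stand in the unseen part of Section 13. Redacted text cannot be counted as absent from the plan.

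Testing both endpoints at two-sided 2.5% would only write down what the plan's figures already suggest. Replacing Bonferroni by a fixed sequence at 5% would be a design preference. If the primary were sized at two-sided 2.5% and tested at 5%, its power at 72 per arm would be Φ(3.0830 − 1.9600) = 86.9%, a surplus and not a loss.

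**Conclusion.** The concern does not hold. It requires that one of two defects be true, and a third reading, the one closest to the text, has neither: 2.5% is half of 5%, it is used for both endpoints, and testing both at two-sided 2.5% gives a familywise error of at most 5.0% with the stated 80% power at 93 per arm and about 85% at 105.

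This rests on two assumptions that the visible text permits but does not state: that 2.5% is two-sided, and that it already includes the Bonferroni division. Across all the readings considered, the upper bound on familywise error runs from 3.75% to 7.5%. Secondary power runs from 71% to 80% at 93 per arm and from 77% to 85% at the current 105. The unfavourable ends come from inferences about redacted text, and the 71% also from a superseded sample size. What is left is unstated detail on sidedness, divisor and primary testing level, which the unredacted plan may well contain.

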### 4.0 BACKGROUND/RATIONALE

PSCs are common and have been reported to be the reason for over 30% of the visits to an outpatient stoma clinic [2]. Peristomal skin problems can cause pain and reduce life satisfaction, and in addition, contribute to higher ostomy product usage, which may raise healthcare costs [3], [4]. It is evident, that maintaining and restoring the integrity of the peristomal skin has important implications.

Hollister Incorporated is marketing a new ostomy product [REDACTED] skin barrier is designed to maintain adhesive properties [REDACTED]

The purpose of this study is to demonstrate how the use of [REDACTED] impacts stoma related cost of care and peristomal skin condition. It is hypothesized that the [REDACTED] barrier improves peristomal skin condition by reducing the incidence [REDACTED] of PSCs which would manifest itself as an overall reduction in the stoma related cost of care.

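### Section 12.6: where 5% is split equally over the Bonferroni family, Holm's procedure would give the secondary endpoint more power at the same familywise error (a cheap improvement, not an error)

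*Combined protocol and SAP*

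**What the plan says.** Section 12.6 covers multiplicity in three visible statements. For the primary objective, Dunnett's test "will be used to assess whether there is any significant difference between" groups whose names are redacted. For the secondary objective, "A Bonferroni correction will be used to adjust the secondary endpoint". Everything else "will be assessed against an unadjusted alpha of 0.05" unless stated otherwise. The visible text does not give the number of hypotheses in the Bonferroni family, and it mentions no step-down or gatekeeping procedure.

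Section 13.1 sizes the trial for "80% power with a 2.5% type 1" error. The numbers required "would be 72 per arm completed for the primary endpoint and 93 completed per arm for the secondary endpoint". The larger was taken: "In order to cover both primary and secondary endpoints, an initial sample size of 93 completed per arm was chosen". Sections 13.1 and 13.5 report that the target was later raised to 105 per arm after an interim analysis. Section 13.5 ties that increase to 80% conditional power and schedules one more look.

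Section 4.0 links the two endpoints: fewer PSCs are expected to improve the skin, "which would manifest itself as an overall reduction in the stoma related cost of care".

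**The concern.** The secondary endpoint set the initial sample size (93 per arm, against 72 for the primary), so the way its type 1 error is protected bears directly on enrolment. A single-step Bonferroni correction tests it at 2.5% even when the primary has already been rejected. Holm then tests it at 5%, at the same familywise error and under any dependence between the endpoints. By the reasoning in 4.0, both effects should be present together, and that is where Holm gains most. At stake is the chance that a real reduction in PSCs is missed because its p-value falls between 2.5% and 5% in a trial that has already shown a cost effect.

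**Working it through.** **Inputs from the documents.** 72 and 93 completed per arm for 80% power at 2.5% (13.1); 105 per arm (13.1, 13.5). The sidedness of the 2.5% is not stated. It is taken as two-sided because the primary alternative in 13.1 is that the test mean "is not equal to that of the control".

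**Assumptions.** Two hypotheses with 5% split equally; the original design effects hold on both endpoints; normal test statistics with correlation ρ from 0 to 0.8; no interim alpha spending; no Dunnett adjustment.

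**Plan's own figures.** The cost difference, its standard deviation and the PSC rates are redacted, so 72 and 93 cannot be reproduced independently. They are used to back out the implied effects. As a check, a two-proportion formula returns 93 per arm for several rate pairs, such as 50% against 28% or 30% against 11.7%. Power from these pairs agrees with the results below within 0.5 point.

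**Step 1, expected test statistic at the planned n.** z(0.9875) + z(0.80) = 2.2414 + 0.8416 = 3.083, at n = 72 for the primary and n = 93 for the secondary. It scales with √n.

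**Step 2, at 105 per arm.**
- Primary: 3.083 × √(105/72) = 3.723. Power at 2.5% = Φ(3.723 − 2.241) = 93.1%.
- Secondary: 3.083 × √(105/93) = 3.276. Power at 2.5% = Φ(3.276 − 2.241) = 84.95%. Power at 5% = Φ(3.276 − 1.960) = 90.59%.

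**Step 3, gain from Holm.** Holm differs from Bonferroni for the secondary only when the primary has p ≤ 0.025 and the secondary has 0.025 < p ≤ 0.05. At ρ = 0 the probability is 0.931 × (90.59 − 84.95) = 0.931 × 5.64 = 5.2 points.

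**Step 4, at 93 per arm.** Primary power is Φ(3.083 × √(93/72) − 2.241) = 89.7%. Secondary power is 80.0% at 2.5% and 86.93% at 5%. The gain at ρ = 0 is 0.897 × 6.93 = 6.2 points.

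**Step 5, correlation (bivariate normal).**

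| n per arm | Secondary, Bonferroni | Gain at ρ = 0 | 0.3 | 0.5 | 0.8 | Secondary, Holm |
|---|---|---|---|---|---|---|
| 93 | 80.0% | 6.2 | 5.9 | 5.6 | 5.5 | 85.5 to 86.2% |
| 105 | 85.0% | 5.2 | 5.0 | 4.8 | 4.6 | 89.6 to 90.2% |

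If the 2.5% is one-sided, the gains are 5.0 to 5.8 points at 105 and 5.8 to 6.8 at 93.

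**Step 6, weaker primary effect (105 per arm, ρ = 0).** At half the design effect, primary power is Φ(3.723/2 − 2.241) = Φ(−0.380) = 35.2%, so the gain is 0.352 × 5.64 = 2.0 points. With no primary effect it is 0.025 × 5.64 = 0.1 point.

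**Step 7, error control.** If both nulls are true, each procedure makes a false rejection exactly when the smaller p-value is at most 0.025, so their familywise error is identical. Under independence it is 1 − 0.975² = 0.0494; simulation gave 0.0495 at ρ = 0 and 0.046 at ρ = 0.5. If only one null is true, Holm tests it at no more than 5%.

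**The case against.** The strongest objection is that the procedure is only partly visible. The opening of 12.6 is redacted, no analysis section for the secondary objective can be read, and 2.5% = 5%/2 is an inference. Read literally, the primary could be tested by Dunnett at the full 5% with only the secondary reduced. Holm across both endpoints would then not be a pure gain: with primary p = 0.04 and secondary p = 0.20, the primary succeeds under that reading and fails when the smaller p-value is compared with 2.5%. That reading would raise its own familywise-error question, but the objection stands and limits where the change applies.

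A reader might infer that the plan throws away about 5 points of secondary power for nothing. The documents do not support that:
- The 80% target was calculated at 2.5%, so the cost of the correction is already in the 93 per arm.
- The gain depends on the primary being rejected, and 13.5 itself says the product's impact in this population is poorly known.
- Single-step Bonferroni gives simple simultaneous confidence intervals and a secondary threshold that does not depend on the cost result.

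A reader might also take 85% as the plan's own secondary power at 105 per arm. It is not. The increase to 105 was made after an interim analysis to maintain 80% conditional power, whereas the 85% carries the original design effects forward.

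Finally, one interim analysis has already shaped the design, and no spending function is visible. Changing the alpha allocation now takes more than one edited sentence. That stands as a condition on how the change is made. None of these points makes Holm worse than Bonferroni where alpha is split equally.

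**Conclusion.** The point holds as a cheap improvement. Bonferroni is a valid choice and the plan contains no error here. Where 5% is split equally over the Bonferroni family, Holm has the same familywise error and rejects everything Bonferroni rejects, sometimes more. For a family of primary plus secondary, with the original design effects on both endpoints, the secondary gains 4.6 to 5.2 points at 105 per arm (from 85.0% to about 90%) and 5.5 to 6.2 at 93. At 105 per arm this shrinks to about 2 points at half the primary effect and to about 0.1 with none; it is never negative. The size rests on the inferred two-hypothesis family and ignores interim spending and the Dunnett step.

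**What to change.** 1. State in 12.6 which hypotheses form the Bonferroni family and how alpha is divided among them.
2. Where alpha is split equally across that family, replace Bonferroni with Holm. For two hypotheses: *the smaller p-value is compared with 2.5%; if that hypothesis is rejected, the other p-value is compared with 5%.* Where Dunnett applies to the primary, its Dunnett-adjusted p-value enters this procedure.
3. If the primary is in fact tested at the full 5%, leave it there and apply Holm only within the family that Bonferroni covers.
4. State how alpha passes from one hypothesis to the other at the interim boundaries.
5. Make the change by amendment before the additional interim analysis in 13.5, by staff without access to unblinded interim results.

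The cost is an amendment and the interim alpha-passing rule, with no extra subjects. The downsides are that simultaneous confidence intervals matching Holm are less simple than Bonferroni's, and that the interim rules become somewhat more complex.
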